9.4.4.1. RSV very severe LRTI start date

Start dates will be defined as the earliest start date of cough or difficulty breathing as described in section [9.4.2.1](#).

9.4.4.2. RSV very severe LRTI end date

End dates will be defined as the latest end date of cough or difficulty breathing as described in section [9.4.2.2](#).

9.4.5. RSV Hospitalization

RSV hospitalization is determined if both the following criteria are met:

- Confirmed RSV infection with nasal swab test from central GSK lab.

AND
- Hospitalization for acute medical condition determined in Inpatient and worsening flag form. Variables will be pulled from [frmINPATIENT_WORSE_FLG] (field [HOSPI_YN]= 'Yes').

9.4.5.1. RSV Hospitalization start dates

Hospitalization start date will be determined from the Inpatient Care form. Variables will be pulled from [frmINPATIENTCARE] (field [HOSP_SRDAT]=)

9.4.5.2. RSV Hospitalization end dates

Hospitalization end date will be determined from the Inpatient Care form. Variables will be pulled from [frmINPATIENTCARE] (field [HOSP_ENDAT]=)

9.4.6. All cause RTI

All cause RTI is reported if the child has one or more of the following symptoms:

- Runny nose reported during the case assessment visit. Variables will be pulled from [frmSURVEILLANCE_CONTACT] (field [ASSESS_VIS]= 'YES') and [frmSYMPTOMS_RTI] (fields [ASSESS_VIS]= 'Yes' and [sctSYMPTOMS_RTI]= 'RUNNY')
- Blocked nose reported during the case assessment visit. Variables will be pulled from [frmSURVEILLANCE_CONTACT] (field [ASSESS_VIS]= 'YES') and [frmSYMPTOMS_RTI] (fields [ASSESS_VIS]= 'Yes' and [sctSYMPTOMS_RTI]= 'BLOCKED')
- COUGH reported during the case assessment visit. Variables will be pulled from [frmSURVEILLANCE_CONTACT] (field [ASSESS_VIS]= 'YES') and [frmSYMPTOMS_RTI] (fields [ASSESS_VIS]= 'Yes' and [sctSYMPTOMS_RTI]= 'COUGH')

9.4.6.1. All cause RTI start date

- Start dates of all cause RTI cases will be the earliest dates of cough, runny nose, or blocked nose. Variables will be pulled from [frmSURVEILLANCE_CONTACT] (field [ASSESS_VIS]= 'YES') and [frmSYMPTOMS_RTI] (fields [ASSESS_VIS]= 'Yes' and
- [sctSYMPTOMS_RTI]= 'Cough' and [cmpCOUGH_DT]= 'SRDAT'
OR
- [sctSYMPTOMS_RTI]= 'Blocked' and [cmpBLOCKED_DT]= 'SRDAT'
OR
- [sctSYMPTOMS_RTI]= 'RUNNY' and [cmpRUNNY_DT]= 'SRDAT')

9.4.6.2. All cause RTI end date

End dates of all cause RTI cases will be the lastest dates of Cough. Variables will be pulled from [frmSURVEILLANCE_CONTACT] (field [ASSESS_VIS]= 'YES') and [frmSYMPTOMS_RTI] (fields [ASSESS_VIS]= 'Yes' and [sctSYMPTOMS_RTI]= 'Cough' and [cmpCOUGH_DT]= 'ENDAT')

9.4.7. All cause LRTI

All cause LRTI is reported if the child has one or more of the following:

- COUGH reported during the case assessment visit. Variables will be pulled from [frmSURVEILLANCE_CONTACT] (field [ASSESS_VIS]= 'YES') and [frmSYMPTOMS_RTI] (fields [ASSESS_VIS]= 'Yes' and [sctSYMPTOMS_RTI]= 'COUGH')
- Difficulty breathing reported during the case assessment visit. Variables will be pulled from [frmSURVEILLANCE_CONTACT] (field [ASSESS_VIS]= 'YES') and [frmSYMPTOMS_RTI] (fields [ASSESS_VIS]= 'Yes' and [sctSYMPTOMS_RTI]= 'BREATHING')

AND

(The data for below can be pulled from the Case Assessment Visit OR Worsening Visits. If worsening visits took place for this episode, the most severe value of SpO₂ or RR will be used, whether it was observed in the Case Assessment Visit or the Worsening Visit.)

- SpO₂(<95% if altitude ≤2500m and <92% if altitude >2500m) during the physical examination of case assessment visit. (field [scOXYGEN_SATURATION_RTI] OR [scOXYGEN_SATURATION_WOR]=[SpO₂]< '95.0%' or <92%)
OR
- RR increase (field [sctRESPIRATORYRATE_RTI]=[VSORRES_RESP] OR [sctRESPIRATORYRATE_WOR]=[VSORRES_RESP_WOR])

RR increase defined as:

- > 60/minute (< 2 months of age)
- > 50/minute (2 to < 12 months of age)
- > 40/minute (12 to 24 months of age)

9.4.7.1. All cause LRTI start dates

The start date of all cause LRTI with the earliest of the start dates of the following symptoms:

- Cough

Variables will be pulled from [frmSURVEILLANCE_CONTACT] (field [ASSESS_VIS]= 'YES') and [frmSYMPTOMS_RTI] (fields [ASSESS_VIS]= 'Yes' and [sctSYMPTOMS_RTI]= 'COUGH' and [cmpCOUGH_DT]= 'SRDAT')

- Difficulty Breathing

Variables will be pulled from [frmSURVEILLANCE_CONTACT] (field [ASSESS_VIS]= 'YES') and [frmSYMPTOMS_RTI] (fields [ASSESS_VIS]= 'Yes' and [sctSYMPTOMS_RTI]= 'BREATHING' and [cmpBREATHING_DT]= 'SRDAT')

9.4.7.2. All cause LRTI end dates

The end date of all cause LRTI is the latest of the end dates of the following symptoms:

- Cough

Variables will be pulled from [frmSURVEILLANCE_CONTACT] (field [ASSESS_VIS]= 'YES') and [frmSYMPTOMS_RTI] (fields [ASSESS_VIS]= 'Yes' and [sctSYMPTOMS_RTI]= 'COUGH' and [cmpCOUGH_DT]= 'ENDAT')

- Difficulty Breathing

Variables will be pulled from [frmSURVEILLANCE_CONTACT] (field [ASSESS_VIS]= 'YES') and [frmSYMPTOMS_RTI] (fields [ASSESS_VIS]= 'Yes' and [sctSYMPTOMS_RTI]= 'BREATHING' and [cmpBREATHING_DT]= 'ENDAT')

Figure 2 Derivation of RSV-LRTI events date and duration according to the the corresponding LRTI event

[figure not shown]

Figure 3 Derivation of RSV-Hospitalization events date and duration

[figure not shown]
[figure not shown]

[figure not shown]
Figure 4 Derivation of RSV-LRTI hospitalization events date and duration according to the corresponding LRTI event

9.4.8. New RSV LRTI episode rule

A new episode of an event is a single case of RSV RTI, RSV LRTI, severe RSV LRTI, or hospitalization meeting the respective case definitions and severity scale with an interval of at least 7 symptom free days since the last episode that was diagnosed. (Note: persistent runny nose is an exception to the 7 symptom free days rule. A child may have persistent runny nose but still present with a new episode of RSV LRTI). If symptoms worsen within 7 days, the subject comes for a worsening visit.

Figure 5 Derivation of 2 RSV LRTI events date and duration with a symptom free period of at least 7 days

9.4.9. Symptoms

9.4.9.1. Increased respiratory rate

The subject will be considered to have increased respiratory rate if one of the following statements is reached:

- Respiratory rate (field [sctRESPIRATORYRATE_RTI])
- > 60/minute for subjects <2 months of age (fields [sctDEMOGRAPHY.itmDOB_RAW] and [rscRESPIRATORYRATE_RTI.VSORRES_RESP])
- > 50/minute for subjects 2-11 months of age(fields [sctDEMOGRAPHY.itmDOB_RAW] and [rscRESPIRATORYRATE_RTI.VSORRES_RESP])
- > 40/minute for subjects 12-24 months of age(fields [sctDEMOGRAPHY.itmDOB_RAW] and [rscRESPIRATORYRATE_RTI.VSORRES_RESP])

Please note that respiratory rate is measured during the general and obstetric physical exam.

9.5. Statistical Methods

9.5.1. Computation of incidence rates

For each endpoint, the incidence rate (IR, number of episodes/endpoints per 100 person-years) will be calculated by dividing the number of subjects reporting the first episode over the follow-up period by the total person-year. A 95% CI will be computed using an exact method for a Poisson variable as described below.

The person-time at risk for an event of interest (RSV-LRTI or RSV hospitalization) will be calculated as the time between the date of birth and the end of the at-risk period or the earliest of the followings:

- Date of first diagnosis of event of interest (e.g. first episode of RSV-LRTI);
- Date when child reaches 1 year (or 6 months if analysis is done during the interim analysis);
- Date of death;
- Date of last follow-up in study.

Please note that in a case where a subject comes to an assessment visits, has LRTI symptoms, is not confirmed for RSV infection via a nasal swab (because either no nasal swab was taken or the lab yielded invalid results), then we will consider the subject as not have a laboratory-confirmed event. The Subject will therefore be censored at the event ($n=0$, $T=$ from start of the follow-up period at risk up to event).

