2. STUDY DESIGN

2.1. Summary

This is a prospective multi-country cohort study that aims to provide information for subsequent clinical trials for maternal immunization for respiratory syncytial virus (RSV). The study will provide background rates of maternal and neonatal events of interest, incidence rates of lower respiratory tract illnesses associated with RSV (RSV LRTI), and will determine the capacity of future sites for clinical trials. Approximately 2300 pregnant women from nine different countries will be enrolled during their third trimester of pregnancy and followed until 42 days after delivery. Their children will be followed from birth until one year of age. Epoch 1 of the study consists of the screening of maternal subjects. Epoch 2 includes visits 1-6 of the mother and visits 1-2 of the new born; during which time data on pregnancy outcomes and maternal and neonatal events of interest will be collected and RSV LRTI surveillance will begin (from visit 1 of the new born). Neonatal events of interest will only include events that occurred during the first 28 days of life, but data on these events can be collected up to one year of age. Maternal and cord blood samples will also be collected from the mother at delivery. Lastly, Epoch 3 will include RSV LRTI surveillance as well as continued recording of neonatal events of interest. During surveillance in Epoch 3, symptoms relevant to RSV illness will be recorded in diary cards, and RSV positivity will be confirmed via laboratory tests performed on nasal swabs collected during site visits.

Please note that when referring to epochs in the SAP, we are following the convention outlined in the protocol. Epochs in the CDISC T domains are named differently and are as follows: For maternal subjects: screening epoch and study procedures epoch. For infants: screening epoch and surveillance epoch (infants do not actually have a screening visit in this study but this is the naming standard used for CDISC T domains).

Figure 1 Study design

D = day; M = month; V = visit; W = week; Y = year. NB = newborn; GA = Gestational age; BS = blood sample; US = urine sample for dipstick testing; IMM = immune response; HB = hematology/biochemistry; RBC = red blood cell(s); WBC = white blood cell(s); RSV = respiratory syncytial virus; RTI = respiratory tract illness; LRTI = lower respiratory tract illness;

Refer to [Table 1](#) for additional information about the analyses indicated above.

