- Sampling schedule for **neonates/infants:** Surveillance for RSV LRTI will be conducted in infants through the 12 month study period. During this 1-year post-birth surveillance period, for each RTI with suspicion of difficulty in breathing, or wheezing, or with parental concern, a nasal swab will be collected at a visit to assess potential RSV associated RTIs/LRTIs.
- Primary Completion Date (PCD): 42 days post-delivery/birth (i.e. Visit 6 for maternal subjects and Visit 2-NB for infant subjects) or last visit of Epoch 002.
- End of Study (EoS): Last testing results released of samples collected up to Visit 4-NB (assays related to primary and secondary endpoints).
- Duration of the study: Approximately 4.5 to 6 months for maternal subjects; approximately 1 year for infant subjects.
 - Epoch 001: Screening
 - Epoch 002: Primary starting at Visit 1 and ending 42 days post-delivery/birth (Visit 6 for maternal subjects and Visit 2-NB for infant subjects).*
 - Epoch 003: Follow-up of infants starting 43 days post-delivery/birth and ending at Visit 4-NB (1 year post-birth).

*Any safety and disease surveillance data collected after Visit 2-NB will be collected in Epoch 003.

Table 2 Study groups and epochs foreseen in the study

Study Groups	Number of subjects enrolled	Age (Min/Max)	Epochs		
			Epoch 001	Epoch 002	Epoch 003
Maternal subjects	Up to ~ 2300	18 years - 45 years	x	x	
Infants	Up to ~ 2300	NA		x	x

Approximately 200 to 300 per country. To achieve the enrollment targets noted above, the number of pregnant women SCREENED in each country may exceed the country-specific enrolment goal.

- Surveillance for pregnancy outcomes and pregnancy-related events of interest that occur from Visit 1 up to 42 days after delivery (Visit 6).
- Surveillance for neonatal events of interest that occur from birth up to 28 days of age.
- Surveillance for RSV LRTI and RSV hospitalization in infants, from birth up to 1 year of age. Nasal swabs will be collected during surveillance visits to confirm RSV positivity.

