3.2.2. Secondary Endpoints

- Pregnancy related events of interest from Visit 1 through Visit 6 (as defined in primary endpoints) for each GAIA level of diagnostic certainty (where applicable and feasible). GAIA levels are explained in detail in Appendix D of the study protocol.
- Neonatal events of interest from birth through 28 days of age (as defined in primary endpoints) for each GAIA level of diagnostic certainty (where applicable and feasible).

Of note, some events of interest fall under a single category but have multiple subcategories. For each event, the investigator should identify the event and select the applicable sub-category and the GAIA level of diagnostic certainty.

- RSV-A neutralizing antibody titres in maternal blood at delivery
- RSV-A neutralizing antibody titres in cord blood at delivery.
- Episode(s) of RSV-LRTI from birth up to 1 year of age.
- Episode(s) of RSV hospitalization from birth up to 1 year of age.

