4.1.3.2. Neonates (infants)

The infant PPS will include all neonates / infants

- *born to pregnant women in the PPS and*
- *who* meet all eligibility criteria up to the time of their censoring, either at study completion or prematurely as drop-out (e.g. withdrawn consent, lost-to-follow-up) who have at least one time point evaluation.

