4.2.3.2. Infant Excluded Subjects

A subject will be excluded from the infant PPS analysis under the following conditions

Code	Condition under which the code is used
900	
Invalid informed consent or fraud data.
 
 Infants who were in utero at the time maternal (and paternal, if required) informed consent was given, and who are live-born. If local law requires it: Written or witnessed/thumb printed informed consent for study participation of the infant obtained from parent(s)/LAR(s) within 10 days of birth.
2010	
Protocol violation (inclusion/exclusion criteria)
 
Inclusion criteria for enrolment:
 
 If infant marked as “No” for the following question in the ELIGIBILITY CHECK_NB screen [frmELIGIBILITYCHECK_NB]: 
 Did the subject meet all the entry criteria? [Eligible]

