Considering all infants followed from visit 1-NB to visit 4-NB, the percentage of subjects with at least one LRTI illness, exact 95% CI will be presented.

Incidence rates of LRTI illnesses will be calculated, with exact 95% CI.

Frequencies of repeat occurrences of LRTI will be tabulated.

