5.3.6.2. Additional considerations

A correction from the analysis planned in protocol in section 5.3.6.1 is that we will be reporting on all cause LRTIs and RSV associated LRTIs.

This analysis will be based on the infant PPS and will be done on the first episode of all, of severe, and of very severe RSV LRTIs (Section 2.2).

Incidence analyses will be performed overall, by country and by age strata (0-2 months, 0-5 months, and 0-11 months). If applicable (in the case of low numbers of incidence), incidence analyses will also be presented by region (Section 9.3). Incidence rates will also be calculated in one-month intervals from birth to one year of age, please see the monthly infant age intervals in Section 9.3.

The analysis of RSV disease incidence is summarized in the table below showing endpoints and analytic methods, these include incidence rate, proportion affected, and incidence proportion.

Incidence rate is the number of first events per person time. Incidence proportion is the number of first RSV LRTI over population at risk during the specified time period (0-2 months, 0-5 months and 0-11 months). Proportion affected is the number of subjects with at least one episode of RSV LRTI at age interval over the total number of subjects at the start of the age interval.

For each of the RSV LRTI endpoints listed in [Table 11](#), the 95% CI will be computed as described in section [9.5.2](#). Kaplan-Meier curves presenting the cumulative probability of the first episode will be displayed overall. The cumulative probability of presenting the first episode will be given with its 95% CI at the end of the follow-up.

Frequencies of repeat occurrences of RSV LRTI, severe LRTI and very severe LRTI will be tabulated.

Cumulative incidence will be presented from birth to one year of life by monthly intervals (Subgroups in section [9.3](#)).

Table 6 Summary of RSV incidence analyses for RSV LRTI of infants from birth to 1 year (Visit 1-NB to visit 4-NB)

Endpoints	Incidence analysis method	Subgroup
All RSV LRTI Severe RSV LRTI Very Severe RSV LRTI	Incidence rates of first episode Cumulative probability of first episode (Kaplan Meier)	Overall, by country, and by age strata
All RSV LRTI Severe RSV LRTI Very Severe RSV LRTI	Proportion affected by all new episodes	Overall, by country, and by age strata
All RSV LRTI Severe RSV LRTI Very Severe RSV LRTI	Incidence proportion of first episode	Overall and by country within each age strata)

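### Person-time for the RSV rates starts at birth with no late-entry rule, and the SAP is inconsistent on when surveillance starts; for infants who enter after birth, the youngest-age rates come out too low

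*SAP*

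**What the plan says.** All references are to the current SAP (Amendment 2).

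- **Denominator.** Section 9.5.1: time at risk "will be calculated as the time between the date of birth and the end of the at-risk period". The rule lists what can end follow-up, but birth is the only start, and no entry date is used.
- **Start of surveillance, first statement.** The opening paragraph of section 2.1: "RSV LRTI surveillance will begin (from visit 1 of the new born". Sections 5.3.6.1 and 5.3.7.1, which restate the protocol's analyses, use the same window: "Considering all infants followed from visit 1-NB to visit 4-NB".
- **Start of surveillance, second statement.** The design list later in section 2.1: "Surveillance for RSV LRTI and RSV hospitalization in infants, from birth up to 1 year of age". Section 3.2.2 agrees: "Episode(s) of RSV-LRTI from birth up to 1 year of age". The title of Table 6 treats the two starts as one: "Summary of RSV incidence analyses for RSV LRTI of infants from birth to 1 year (Visit 1-NB to visit 4-NB".
- **Entry of the infant.** Section 4.2.3.2 refers, where local law requires it, to "informed consent for study participation of the infant obtained from parent(s)/LAR(s) within 10 days of birth". The infant enrolled set needs a valid signed consent (4.1.2.2), and the infant per-protocol set takes infants "who have at least one time point evaluation".
- **What makes an event.** RSV-LRTI needs symptoms reported at a case assessment visit and a positive nasal swab (9.4.2). RSV hospitalization needs a positive swab from the sponsor's central laboratory and a flag on the inpatient and worsening form (9.4.5).

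The interval between birth and Visit 1-NB is not given in the SAP text.

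**The concern.** If an infant comes under surveillance some days after birth, those days sit in the denominator while the study has almost no means of confirming an event in them. An infant who dies or is lost before consent and a first evaluation is left out of the analysis set, whereas each late-entering infant who is kept is credited with the pre-entry days. For those infants it is immortal time, and the resulting error always makes the rate too low.

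The error falls where the study most needs the figures. Section 5.3.6.2 plans rates in one-month intervals from birth, by age stratum and by country. Section 5.4.2.2 confines the cord-blood antibody analysis to 0-2 and 0-5 months. The study exists to inform maternal RSV immunization trials (2.1). Because post-birth consent depends on local law, the size of the error could also differ between countries.

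**Working it through.** The SAP states no expected rate, event count or precision for these endpoints, so there is no figure of its own to reproduce. The check is a sensitivity calculation.

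**Inputs**
- g, days from birth to entry: not in the SAP text. I take 0, 1, 3 and 10; 10 is the consent limit in section 4.2.3.2.
- f, share of infants with that gap: not in the SAP. I take 100% (upper bound) and 25% (assumption).
- L, length of the age interval: 30 days for month 0, 91 for 0-2 months, 365 for 0-11 months. Section 9.3 prints 0-30 days beside the 0-2 month stratum, which conflicts with its own verbal definition; I use the three months that the words describe.
- A low, constant hazard within each interval, and no events counted before entry.

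**Formula.** With N infants and hazard h per year, expected events are h × N × (L − f·g)/365. Section 9.5.1 divides by N × L/365. The planned rate is therefore h × (1 − f·g/L), an understatement of f·g/L.

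| f | g (days) | Month 0 | 0-2 months | 0-11 months |
|---|---|---|---|---|
| any | 0 | 0% | 0% | 0% |
| 100% | 1 | 1/30 = 3.3% | 1/91 = 1.1% | 1/365 = 0.3% |
| 100% | 3 | 3/30 = 10.0% | 3/91 = 3.3% | 3/365 = 0.8% |
| 100% | 10 | 10/30 = 33.3% | 10/91 = 11.0% | 10/365 = 2.7% |
| 25% | 10 | 2.5/30 = 8.3% | 2.5/91 = 2.7% | 2.5/365 = 0.7% |

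**Against sampling error.** Take 2300 infants (Table 2), an assumed rate of 5 per 100 person-years, every infant entering on day 10, and the exact Poisson limits of section 9.5.2.
- 0-2 months: person-years are 2300 × 91/365 = 573.4 from birth and 2300 × 81/365 = 510.4 from entry. With 26 events the rates are 4.53 (95% CI 2.96 to 6.64) and 5.09 (3.33 to 7.46).
- Month 0: person-years are 189.0 and 126.0. With 6 events the rates are 3.17 (1.16 to 6.91) and 4.76 (1.75 to 10.36).

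**Between countries.** If all infants in one country entered on day 10 and all in another at birth, with the same true hazard, the month-0 rate in the first would appear as 1 − 10/30 = 0.67 of that in the second. This is an extreme case; the SAP does not say which countries need post-birth consent.

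**The case against.** The strongest reply is that no gap is shown. Section 2.1 also says that surveillance runs from birth, section 3.2.2 defines the endpoints from birth, and the Table 6 title equates birth with Visit 1-NB. Sections 5.3.6.1 and 5.3.7.1 only restate the protocol and set no origin for person-time. The design figure, which may give the timing of Visit 1-NB, is not reproduced in the text available. This stands, and it is why every size above is conditional.

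A reader might go further and infer one or more of the following. The documents do not support them.

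- *All infants carry immortal time and month-0 rates are a third too low.* That needs every infant to enter on day 10. The 10 days are a maximum for consent, apply only where local law requires a separate consent, and are not the date of Visit 1-NB.
- *The pre-entry days are event-free by construction.* Section 9.4.2.1 takes onset dates from the parents' history, so an illness that began before entry can be assessed and swabbed afterwards. An event is hard to confirm in those days, not impossible.
- *The Kaplan-Meier and Cox results are biased to the same degree.* Both depend on the risk sets at event times. Days without events before a common entry time contribute nothing. Only different entry ages combined with events in the first days could matter, and little change is expected.

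It can also be said that these are secondary, descriptive estimates and that the 0-2 month shift lies well inside its confidence interval. That limits the importance of the point but does not remove it: the error has one direction and the exact limits do not reflect it.

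**Conclusion.** The point holds in conditional form. Two things are certain from the text: section 2.1 gives two starts for surveillance, and section 9.5.1 has no rule for infants who enter after birth, although section 4.2.3.2 allows consent up to 10 days later in some places. For such infants the rates in the youngest intervals are too low.

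How much too low depends on the share and timing of late entry, which the SAP text does not give. The plausible range runs from nothing to the day-10 upper bound in the table. Month 0 is the only interval where the change could be large; the 0-11 month rate moves by at most about 3%. A distortion between countries is possible but not established. These sizes assume a constant hazard within each interval and no confirmed events before entry.

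**What to change.** 1. In section 2.1, reconcile the two statements of when surveillance starts and say how Visit 1-NB relates to birth.
2. In section 9.5.1, start person-time at the later of birth and entry into surveillance, entry being Visit 1-NB or, where infant consent is given after birth, that consent.
3. State that an episode with onset before entry but confirmed after it is left out of the main rate and listed separately.
4. Report entry age by country, and keep the from-birth calculation as a sensitivity analysis.
5. Use the same entry time, on the age scale, in the Kaplan-Meier and Cox analyses so that all analyses share one origin.

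The cost is a few sentences of SAP text and one derived variable from birth, visit and consent dates that the study already collects. The downside is slightly fewer infant-days in month 0, and any episode that began before entry moves from the main rate to a listing. Where entry is at birth, nothing changes.

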9.4.3. RSV severe LRTI

RSV severe LRTI cases will be reported if the person meets the case definition of RSV LRTI

AND

(The data for below can be pulled from the Case Assessment Visit OR Worsening Visits. If worsening visits took place for this episode, the most severe value of SpO₂ or RR will be used, whether it was observed in the Case Assessment Visit or the Worsening Visit.)

- SpO₂(<93% if altitude ≤2500m and <90% if altitude >2500m) (field [scOXYGEN_SATURATION_RTI] OR [scOXYGEN_SATURATION_WOR]=[SpO₂]<‘93.0% or <90%’)
OR
- Lower chest wall indrawing reported during the physical examination. (field [sctCHEST_INDRAWING_RTI]=[INDRAWING]=‘YES’) OR (field [sctCHEST_INDRAWING_WOR]=[INDRAWING]=‘YES’)

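### The missing-swab censoring rule in SAP 9.5.1 is not endpoint-specific, so, read literally, it can drop later confirmed severe, very severe and hospitalized RSV events from their incidence rates; the likely effect is small

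*SAP*

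**What the plan says.** Section 9.5.1 gives its scope at the start: "For each endpoint, the incidence rate (IR, number of episodes/endpoints per 100 person-years) will be calculated". The next paragraph reads "The person-time at risk for an event of interest (RSV-LRTI or RSV hospitalization) will be calculated" and counts time from birth to the earliest of first diagnosis, "Date when child reaches 1 year", death or last follow-up.

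The last paragraph adds the missing-swab rule. It applies when an infant "comes to an assessment visits, has LRTI symptoms, is not confirmed for RSV infection via a nasal swab". Two reasons for the missing confirmation are named: a swab that was never collected, or a laboratory result that was not valid. The consequence is "The Subject will therefore be censored at the event", with n=0 and time counted up to that point. A valid negative swab does not trigger it. The paragraph does not ask whether the illness was severe or led to admission.

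The endpoints have further criteria that need no swab:

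- Severe RSV-LRTI (9.4.3): "RSV severe LRTI cases will be reported if the person meets the case definition of RSV LRTI", plus SpO2 below the severe cut-off or lower chest wall indrawing.
- Very severe RSV-LRTI (9.4.4): RSV-LRTI plus SpO2 below a lower cut-off, inability to feed, or unresponsiveness.
- RSV hospitalization (9.4.5): confirmed RSV and "Hospitalization for acute medical condition determined in Inpatient and worsening flag form" (HOSPI_YN = Yes). No LRTI criterion is listed.

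Sections 5.3.6.2 and 5.3.7.2 require first-episode incidence for all of these. Proportion affected (9.5.3) and incidence proportion (9.5.4) contain no missing-swab rule.

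**The concern.** Censoring for unknown RSV status makes sense when a swab result could have turned the illness into the event being counted. An unswabbed LRTI with no severe sign cannot be severe RSV-LRTI, and one without an admission cannot be an RSV hospitalization, whatever the swab would have shown. For that endpoint nothing is unknown, yet the rule as worded ends follow-up. A later swab-confirmed severe episode or admission in the same infant then leaves the numerator of the rate, and the remaining person-time leaves the denominator.

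The converse gap concerns RSV hospitalization. Because 9.4.5 does not require LRTI, an infant admitted without LRTI symptoms and without a valid swab may not trigger the rule. That infant stays at risk as event-free although its status for this endpoint is unknown.

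These secondary rates are meant to inform later maternal-immunization trials (2.1). The affected infants are those who have already had an LRTI, so any correlation of risk within infants pushes the rates down. The same later event could also appear in proportion affected and be absent from the rate, although Table 6 reports both for the RSV-LRTI severity endpoints.

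**Working it through.** The SAP states no rate or missing-swab share, so there is no figure of its own to reproduce.

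**One infant.** A non-severe, non-admitted, unswabbed LRTI occurs at month 3 and a swab-confirmed severe RSV-LRTI with admission at month 8.

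- As written: n=0, T = 3/12 = 0.25 years, for both the severe-LRTI and the hospitalization rate.
- Endpoint-specific: n=1, T = 8/12 = 0.67 years, for each.
- Dropped from each rate: one event and 5/12 = 0.42 person-years.

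**RSV hospitalization in a cohort.** About 2300 infants (SAP Table 2), followed for 1 year. The other inputs are assumptions: L LRTIs per infant-year, a share m without a valid swab, 20% of LRTIs admitted, 25% RSV, all independent within an infant.

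- Confirmed RSV hospitalization: s = L × 0.20 × 0.25 × (1 − m).
- Censoring as written, at any unswabbed LRTI: c = L × m.
- Endpoint-specific censoring, at an unswabbed admitted LRTI only: c_a = 0.20 × L × m.
- Total hazard: a = s + c as written, or s + c_a if endpoint-specific.
- Equal risk: first events per infant = s(1 − e^−a)/a. The rate is s under both rules.
- Risk varying between infants (shared gamma frailty, variance 1): first events = s/(1 + a), person-time = ln(1 + a)/a.

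For L = 0.4 and m = 0.10: s = 0.018, c = 0.040, c_a = 0.008, so a = 0.058 as written and 0.026 endpoint-specific.

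- Equal risk: 2300 × 0.018 × 0.9871 = 40.9 events endpoint-specific; 2300 × 0.018 × 0.9716 = 40.2 as written. Loss 1.6%, rate unchanged.
- Frailty: 2300 × 0.018/1.026 = 40.4 against 2300 × 0.018/1.058 = 39.1. Loss 3.0%. Person-time per infant is 0.9872 against 0.9721, so the rate is 1.777 against 1.750 per 100 person-years, 1.5% too low.

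| L | m | Events per 2300, equal risk (endpoint-specific → as written) | Lost | Events per 2300, frailty (endpoint-specific → as written) | Lost | Rate, frailty |
|---|---|---|---|---|---|---|
| 0.2 | 5% | 21.7 → 21.6 | 0.4% | 21.6 → 21.4 | 0.8% | −0.4% |
| 0.4 | 10% | 40.9 → 40.2 | 1.6% | 40.4 → 39.1 | 3.0% | −1.5% |
| 0.8 | 20% | 71.3 → 67.0 | 6.1% | 69.2 → 61.7 | 10.7% | −5.4% |

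Simulation of the same scenarios agrees to within rounding and simulation error.

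**Severe RSV-LRTI, wider assumptions.** Simulated at 3 severe RSV-LRTIs per 100 person-years, 0.2 to 0.5 non-severe LRTIs per infant-year and 5% to 30% without a valid swab. The comparison is with continued follow-up past the unswabbed non-severe LRTI.

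- No frailty: 0.5% to 7% of first events lost, rate essentially unbiased.
- Frailty variance 1: 1.0% to 13% lost, rate 0.5% to 6.6% too low.
- Frailty variance 2: 1.4% to 17% lost, rate 0.9% to 11.5% too low. The upper end needs 30% unswabbed and the higher LRTI rate.

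**Against sampling error.** With 40 events, the exact Poisson interval of 9.5.2 runs from 28.6 to 54.5 events, that is −29% to +36% around the estimate.

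**Admissions without LRTI symptoms.** These calculations generate LRTIs only, so they say nothing about the size of this gap.

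**The case against.** The strongest defence is that 9.5.1 nowhere says an unswabbed LRTI ends follow-up for every endpoint. The event at which the infant is censored can be read as the illness that would have been the endpoint under analysis, and the section's only worked example is a first RSV-LRTI. This stands in part: the broad reach is inferred from the section's scope, its naming of RSV hospitalization and a trigger without further conditions. But nothing in the current SAP states the narrower reading. If the paragraph concerned RSV-LRTI alone, RSV hospitalization would have no missing-swab rule. Either way the text needs to say which is meant.

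A reader might infer that later severe cases and admissions are discarded from the study. The documents do not support that. The paragraph belongs to the incidence-rate computation, and 9.5.3 and 9.5.4 can still count those events. Kaplan-Meier and Cox results are affected only if they use this person-time, which the SAP does not state.

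A reader might also infer that lost events mean a biased rate. They do not in themselves, since person-time is lost with them; with equal risk the rate is unbiased. The plausible central effect is also far inside the sampling error.

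The point about admissions without LRTI symptoms is open to doubt. Section 2.1 describes the inpatient flag within follow-up of a respiratory episode, and 9.4.2 lists cough and difficulty breathing among the LRTI symptoms. If either alone triggers the rule, fewer admissions are missed, though more infants are then censored without need.

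**Conclusion.** The concern holds as a minor defect. Read literally, the rule censors infants whose non-event status for severe RSV-LRTI, very severe RSV-LRTI or RSV hospitalization is already known from 9.4.3 to 9.4.5, and so removes later confirmed events and person-time from those incidence rates.

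At 40 LRTIs per 100 infant-years and 10% without a valid swab, the loss is about 1.5–3% of confirmed RSV hospitalizations, about one event in 41. The rate is too low by under about 2%, and only if infants with an earlier LRTI are at higher risk. Larger effects need a larger missing-swab share or stronger shared risk. The LRTI rate, missing-swab share, admission share, RSV share and frailty are all assumptions.

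The claim that the rule acts on the wrong infants in both directions for RSV hospitalization goes further than the text allows. That an unswabbed admission may stay at risk as event-free is plausible, but it depends on how LRTI symptoms are read and has not been quantified.

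**What to change.** Restate the last paragraph of 9.5.1 per endpoint. For a given endpoint, censor an infant only at an illness that meets all of that endpoint's non-virological criteria and has no valid swab result:

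- RSV-LRTI: the LRTI criteria.
- Severe or very severe RSV-LRTI: the LRTI criteria plus a severe or very severe criterion.
- RSV hospitalization: HOSPI_YN = Yes, with or without LRTI.

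At any other unswabbed illness, follow-up for that endpoint continues. Use the same censoring variable wherever Kaplan-Meier or Cox analyses rely on this person-time.

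The cost is one paragraph of SAP text and one censoring variable per endpoint. It needs no new data.
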